## **5.10 Analysis of Efficacy Variables**

All primary and secondary efficacy parameters, see section 3, will be summarized descriptively and no formal statistical analyses will be performed. The analyses will be performed by treatment group and overall, for both the FAS and PPS set using appropriate descriptive statistics. The results of the spirometry will also be presented over time, i.e. baseline, 30-, 60- and 90-minutes post baseline.

### **Explorative / Sub-group analysis**

Summary statistics of the primary and secondary endpoints may also be presented for specific sub-groups, if the number of patients in these sub-groups are high enough to allow a meaningful interpretation of the results.

## **5.11 Analysis of Safety Variables**

These analyses will be conducted for the safety set (SS) only and no formal statistical testing will be performed in the safety endpoints.

## **Adverse Events**

For the safety analysis only adverse events with an onset after the first administration of the study medication (TEAEs) will be displayed in summary tables. AEs starting before the first administration will be listed only. Adverse event summaries will be presented by treatment group and overall. An overall summary of AEs will be produced including the number of TEAEs; the number and % of subjects reporting at least 1 TEAE, serious TEAE (where SAE is reported as 'Yes'), TEAE leading to withdrawal from the study and the number and % of subjects reporting TEAEs by severity and relationship to study drug. A subject with multiple occurrences of the same AE is counted only once at the maximum level of severity or the highest association to study drug.

Adverse events will be coded using MedDRA and will be presented on the MedDRA preferred term (PT) level.

The tables will list for each adverse event, the number of events and the number and percentage of patients in each treatment group in whom the event occurred. Adverse events will be grouped by system organ class.

All serious adverse events (SAEs) will be listed separately.

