	
Part 2: Expansion Phase
 
Once the Recommended Therapeutic Dose has been determined in Part 1 (a), a minimum of 150 patients will be enrolled in to the Expansion Phase, which is split into 3 periods. For participants taking part in the Dose Finding Phase (Part 1), eligibility criteria will be reassessed prior to entering Part 2 of the trial.
 
1) Baseline visit
 
In a minimum of 50 participants the following will be performed:
 

• Administration of a test dose of RESP301, at the RTD

• Assesses response to RESP301 (incl. recording any AEs, FEV1 pre- and post dose and monitoring methaemoglobin levels pre-, during and post- administration, using fingertip sensor; methaemoglobin level should be <=2% before, <=5% during, and <=3% at 30-60 mins post dose (i.e. if still >3% at 30 mins, check again at 60mins post dose).

 
During the visit participants who satisfactorily tolerate the test dose will then be enrolled into the “dormant period” of the study for 12 months.
 
An independent Data Monitoring Committee will review the data from the 50 participants that received the RTD. Based on the data from these participants, it will be decided whether test doses should be administered to further participants before enrolling them into the Dormant Period.
 
2) Dormant Period
 
Dormant period patients are requested at the baseline visit, and monthly follow-up calls, to inform the study team if they develop exacerbation symptoms indicative of a respiratory infection. There will be no other study procedures or data collection during the “dormant study phase” unless the participant experiences exacerbation symptoms.
 
3) Treatment Period
 
A patient who experiences exacerbation symptoms for at least 24 hours should contact the study team as soon as practicable to allow a study interaction to be undertaken remotely (via video link, if possible), within 72 hours of onset of at least one of the following: fever (<math>>38.0^{\circ}\text{C}</math>), systemic malaise, increased cough or wheeze, increased sputum volume or increased purulence. During the remote visit the patient’s symptoms will be discussed and if

--	--

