### 9.2 Time Period and Frequency for Collecting AE and SAE Information

All AEs and SAEs will be collected from signing of informed consent until the last follow-up visit at the time points specified in the SoA (Table 8-1).

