## Appendix 1: Adverse Events: Definitions and Procedures for Recording, Evaluating, Follow-up, and Reporting

### Definition of AE

AE Definition

• An AE is any untoward medical occurrence in a patient or clinical study participant, temporally associated with the use of a study intervention, whether or not considered related to the study intervention.

• NOTE: An AE can therefore be any unfavorable and unintended sign (including an abnormal laboratory finding), symptom, or disease (new or exacerbated) temporally associated with the use of a study intervention.

Events Meeting the AE Definition

• Any abnormal laboratory test results (hematology, clinical chemistry, or urinalysis) or other safety assessments (e.g., ECG, radiological scans, vital signs measurements), including those that worsen from baseline, considered clinically significant in the medical and scientific judgment of the Investigator (e.g., not related to progression of underlying disease).

• Exacerbation of a chronic or intermittent pre-existing condition including either an increase in frequency and/or intensity of the condition.

• New conditions detected or diagnosed after study intervention administration even though it may have been present before the start of the study.

• Signs, symptoms, or the clinical sequelae of a suspected drug-drug interaction.

• Signs, symptoms, or the clinical sequelae of a suspected overdose of either study intervention or a concomitant medication. Overdose per se will not be reported as an AE/SAE unless it is an intentional overdose taken with possible suicidal/self-harming intent. Such overdoses should be reported regardless of sequelae.

• "Lack of efficacy" or "failure of expected pharmacological action" per se will not be reported as an AE or SAE. Such instances will be captured in the efficacy assessments. However, the signs, symptoms, and/or clinical sequelae resulting from lack of efficacy will be reported as AE or SAE if they fulfill the definition of an AE or SAE.

Events NOT Meeting the AE Definition

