### **Follow-up of AE and SAE**

- The Investigator is obligated to perform or arrange for the conduct of supplemental measurements and/or evaluations as medically indicated or as requested by the Sponsor to elucidate the nature and/or causality of the AE or SAE as fully as possible. This may include additional laboratory tests or investigations, histopathological examinations, or consultation with other health care professionals.
- New or updated information will be recorded in the originally completed CRF.
- The Investigator will submit any updated SAE data to the Sponsor within 24 hours of receipt of the information.

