## GLOSSARY OF ABBREVIATION

AE	Adverse Event
ATC	Anatomical Therapeutically Chemical
BMI	Body Mass Index
CCQ	Clinical COPD Questionnaire
CFR	Code of Federal Regulations
CI	Confidence interval
CIOMS	Council for International Organizations of Medical Sciences
COPD	Chronic obstructive pulmonary disease
COVID-19	Coronavirus disease 2019
eCRF	electronic Case Report Form
CRO	Contract Research Organization
CT	Computerized Tomography
DMC	Data Monitoring Committee
DRE	Disease Related Event
ECG	Electrocardiogram
EDC	Electronic Data Capture
FAS	Full Analysis Set
FDA	Food and Drug Administration
GCP	Good Clinical Practice
ICF	Informed Consent Form
ICH	International Council for Harmonization
IDMC	Independent Data Monitoring Committee
IEC	Independent Ethics Committee
IMP	Investigational Medicinal Product
IRB	Institutional Review Board
ITT	Intent To Treat
MedDRA	Medical Dictionary for Regulatory Activities
mHb	Methaemoglobin
NHS	National Health Service
NO	Nitric oxide
NO2	Nitrogen dioxide
NOx	Oxide of nitrogen
PEoT	Post End of Treatment
PR	Pulse Rate
PT	Preferred Term
PP	Per Protocol
QC	Quality Control
RTD	Recommended Therapeutic Dose
SAC	Safety Advisory Committee
SAE	Serious Adverse Event
SAP	Statistical Analysis Plan
SAS	Statistical Analysis system
SD	Standard Deviation

---

SEM	Standard Error of the Mean
SoA	Schedule of activities
SOC	Standard of Care or System Organ Class
SP	Safety population
SpO 2	Oxygen saturation
SUSAR	Suspected Unexpected Serious Adverse Reaction
SOP	Standard Operative Procedure
TEAE	Treatment-emergent adverse event
TID	Three Times Daily
TMF	Trial Master file
VAS	Visual Analogue Scale
WHO-DD	World Health Organization Drug Dictionary

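### SAP 5.11 defines treatment-emergent events by onset date alone, so an AE recorded before the first RESP301 dose that later worsens can miss every AE summary table

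*SAP*

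**What the plan says.** SAP 5.11 (Adverse Events) sets the rule for the safety tables: "only adverse events with an onset after the first administration of the study medication (TEAEs) will be displayed in summary tables". It continues: "AEs starting before the first administration will be listed only". The glossary expands TEAE as "Treatment-emergent adverse event" and defines nothing further. SAP 15.3 plans three AE tables: an overview, one by system organ class, and one by preferred term within class.

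The protocol supplies the rest:

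- Section 9.2, on collection: "All AEs and SAEs will be collected from signing of informed consent until the last follow-up visit", at the time points in the schedule of activities.
- Appendix 1, among events that count as AEs: "Exacerbation of a chronic or intermittent pre-existing condition including either an increase in frequency and/or intensity of the condition".
- Appendix 1, on follow-up: "New or updated information will be recorded in the originally completed CRF".
- Section 10.4.3 plans counts of participants with any AE, any related AE and any SAE, with no limit to treatment-emergent events.

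**The concern.** A treatment-emergent definition normally has two limbs: events that start after dosing, and events already present that get worse after dosing. The SAP has only the first. Collection starts at consent, so some AE records will carry an onset date before the first dose. If such an event then becomes severe or serious after RESP301, an onset-only rule can keep it out of the tables.

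Safety and tolerability is a secondary objective in both documents. The tolerability signs that the SAP names (cough, chest pain or tightness, bronchospasm, dyspnoea) overlap with symptoms that these participants may already have. What is at stake is whether a post-dose deterioration is counted at all in the AE incidence figures, and whether the two sites count it in the same way.

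**Working it through.** No figure in the plan needs reproducing. The check is to follow different kinds of event through the rules.

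**Can pre-dose AE records exist?** Yes. SAP Tables 2 and 3 schedule AE review at Screen 1 in both parts, ahead of the dosing or baseline visit. In Part 1 the window can be short, because a note to SAP Table 2 lets the two screening visits be combined for some patients.

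**Case A: chronic cough in the medical history, worse after RESP301.** Appendix 1 makes the increase in intensity an AE in its own right. Its onset is the worsening, which is after dosing. It is tabulated.

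**Case B: an event that starts after consent and before the first dose, is recorded as a mild AE, and becomes severe or serious after RESP301.** Two routes are open.

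- The site updates the existing record, as the Appendix 1 follow-up text suggests. The onset stays before dosing, so the event is listed only and enters none of the three tables.
- The site treats the worsening as a fresh AE. The onset is after dosing, so it is tabulated.

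Neither document says which route applies. The SAP's severity rule, "A subject with multiple occurrences of the same AE is counted only once at the maximum level of severity", does not help: it works inside tables that already exclude pre-dose onsets.

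**Case C: the exacerbation that opens home treatment.** The protocol synopsis says: "A patient who experiences exacerbation symptoms for at least 24 hours should contact the study team as soon as practicable". These symptoms therefore precede the first home dose. However, SAP Table 3 schedules a review of symptoms, and no AE review, at the pre-treatment call. Appendix 1 also excludes expected symptoms of the disease under study unless they are more severe than expected. Most presenting symptoms should thus never become AE records with a pre-dose onset. For anyone who had a test dose or took part in Part 1, an AE that begins later already follows first administration.

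**Scale.** Only two figures can be derived, and neither estimates the number affected.

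- Participants whose first-ever dose could be taken at home: the synopsis allows up to 100 of 150 to enter Part 2 without a test dose, and SAP section 4 expects 30 of 150 to exacerbate. If all 100 tests are waived and exacerbation is unrelated to test-dose status, this is 30 × 100/150 = 20. If no test is waived it is 0. The range of 0 to about 20 shows how many have the opportunity for a pre-dose AE during an exacerbation, not how many have one that worsens.
- Weight of one participant in a Part 1 cohort: 1/8 = 12.5 percentage points.

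**The case against.** The strongest reply is that little is lost. An ongoing AE may itself be read as a pre-existing condition, so its worsening would be a new AE under Appendix 1. The follow-up sentence is general text and does not say that a worsened event keeps its old onset date. The annotated eCRF, which might settle the matter, is not among the documents. Deterioration also shows elsewhere: all AEs and SAEs are listed, test-dose tolerability in SAP 3.1 has no onset condition and is tabulated with spirometry and VAS in SAP 15.2, and the IDMC reviews safety data on an ongoing basis. This is a small, descriptive, single-arm feasibility study.

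Much of this stands, and it limits the reach of the point. A reader might infer that worsening of the participants' chronic cough, wheeze or dyspnoea is left out of the tables; Case A shows that it is not. A reader might also infer that all of the roughly 30 home-treated participants are affected because each has symptoms before the first home dose; Case C shows that a qualifying symptom is not the same as a recorded AE.

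What does not stand is that the gap is therefore closed. That Appendix 1 can be read either way is the difficulty, because the same event may be counted at one site and omitted at the other. Listings do not give incidence, and the tolerability endpoint covers the test dose, not the home course.

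**Conclusion.** The point holds in a limited form. For AEs recorded between consent and first administration that later increase in intensity or become serious, tabulation depends on an unstated recording choice, and the SAP's stated default leaves them out. The SAP is also narrower than protocol section 10.4.3 without explanation, while the first table in SAP 15.3 is still titled as covering all AEs.

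The number of such events is probably small. It depends on how many AEs are recorded before first dose, how many persist and worsen, and how sites record the change; the documents give none of these. A reader might go on to infer that reported AE incidence is biased downward, especially for respiratory events. The documents show that omission is possible, not that it will occur to any particular extent. The case for change rests on the rule being able to misclassify post-dose harm and on the low cost of correcting it.

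**What to change.** In SAP 5.11, define a TEAE as an AE with onset at or after the first RESP301 administration, or an AE present before it that afterwards increases in intensity or becomes serious, with the date of worsening taken as its onset. In the eCRF completion guidance, state that such worsening is entered as a new record or as a dated change of intensity, so that the rule can be programmed. Add a short explanation of why the tables are limited to TEAEs when the protocol's summaries are not, and align the title of the overview table.

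The cost is one sentence of definition, a brief explanatory note and one line of site guidance. The downside is slightly higher reported AE counts. If records already exist without dated intensity changes, the AEs with pre-dose onset can be reviewed individually before database lock.

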## **VAS Scores**

For each parameter will be summarized by treatment group using descriptive statistics at each time point.

## **5.12 Interim Analysis and Data Monitoring**

There are no planned interim efficacy analyses. However, an Independent Data Monitoring Committee (IDMC) will review the safety data on an ongoing basis.

## **5.13 Revised/Additional Versions**

Not applicable, this is the first version.

## End-of-Text Tables and Figures

The default tables, figures and listings (TFL) layout will be as follows:

Orientation	A4 Landscape
Margins	Top: 2.0 cm Bottom: 2.0 cm Left: 2.0 cm Right: 2.0 cm
Font	Courier New 8pt
Headers (Centre)	Sponsor Protocol Number, TLF Number, Title, Population
Footers (Left)	Source listing, date/time TFL produced and additional clarification

The font size may be reduced as necessary to allow additional columns to be presented, but not at the expense of clarity. Also, the orientation of the table may be changed to portrait if appropriate. At the time of programming footnotes will be added to the listing, table, or figure as needed. All footnotes will be used for the purpose of clarifying the presentation.

The table, listing and figure numbering may be changed depending on the available paper space and variables presented.

## Section 15 End-of-Text Tables and Figures

### 15.1 Demographic and Baseline Characteristics

Table 1.1	Subject disposition – All patients screened
Table 1.2	Study withdrawal – Safety set
Table 1.3	Protocol violations – Safety set
Table 2.1	Gender, age, ethnicity – Safety set
Table 2.2	Height, weight and BMI – Safety set
Table 2.3	Smoking status – Safety set
Table 2.4	COPD and bronchiectasis history – Safety set

Table 3.1	Medical history (MedDRA system organ classes) – Safety set
Table 3.2	Concurrent diseases (MedDRA system organ classes) – Safety set
Table 3.3	Concomitant medications ongoing at baseline – Safety set
Table 3.4	Concomitant medications started after baseline – Safety set
Table 4.1	Summary of physical examination – Safety set
Table 5.1	Compliance with study medication – Safety set

## 15.2 Efficacy Results

Table 1.1	Summary of primary endpoints, part 2 – FAS/PPS set
Table 1.2	Summary of secondary endpoints – FAS/PPS set
Table 1.3	Summary statistics of spirometry over time – FAS/PPS set
Table 1.4	Summary of VAS scales – FAS/PPS set
Table 1.5	Summary statistics of explorative/sub-group analyses, if any – FAS/PPS set

## 15.3 Safety Results

Table 1.1	Overview of all adverse events – Safety set
Table 1.2	Patients with adverse events at MedDRA system organ class level – Safety set
Table 1.3	Patients with adverse events, preferred term grouped by MedDRA system organ class – Safety set

## Appendix 16.2 Subject Data Listings

### Appendix 16.2.1 Subject Disposition

Listing 1	End of study assessment – Safety set
Listing 2	Screening failures – All screened subjects
Listing 3	Subjects treated – Safety set
Listing 4	Protocol deviations - Safety set

### Appendix 16.2.2 Informed Consent, Protocol Deviations, and Inclusion and Exclusion Criteria

Listing 1	Informed consent – Safety set
Listing 2	Inclusion criteria – Safety set
Listing 3	Exclusion criteria – Safety set

### Appendix 16.2.3 Subjects Excluded from Analyses

Listing 1	Reasons for non-eligibility for the Full Analysis Set – Safety set
Listing 2	Reasons for non-eligibility for the Per Protocol Set – Full analysis set

### Appendix 16.2.4 Demographics, Medical History, and Prior/Concomitant Medications

Listing 1	Demographics – Safety set
Listing 2	Medical history – Safety set
Listing 3	Concurrent conditions – Safety set

Listing 4	Prior and concomitant medication – Safety set
-----------	---

### **Appendix 16.2.5 Study Drug Administration**

Listing 1	Treatment received – Safety set
Listing 2.1	Compliance – Safety set

### **Appendix 16.2.6 Efficacy Data**

Listing 1	Primary endpoint, part 2 – Safety set
Listing 2	Secondary endpoints – Safety set
Listing 3	Spirometry – Safety set
Listing 4	VAS scales – Safety set

### **Appendix 16.2.7 Adverse Events**

Listing 1	Adverse events – Safety set
Listing 2	Serious adverse events – Safety set

### **Appendix 16.2.9 Vital Signs, ECGs, and Physical Examination**

Listing 1	Vital signs – Safety set
Listing 2	Physical examination findings – Safety set
Listing 3	Pregnancy test – Safety set
Listing 4	Additional notes (Safety set)
